# 6. EFFICACY AND SAFETY VARIABLES

6.1. Schedule of Assessments

Table 1: Schedule of Assessments for Screening and Vaccine Induction Phase – Part 1

	Screen					Vaccine I	nduction Pl	nase a,b			
	within 14/21 days before	within 7 days before		1st dose		2 nd dose	3 rd dose	4 th dose		5 th dose	
	1 st dose (-1 – -14/-21)	1 st dose (-17)	Day	Day 1 (-	Day 3	Day 8 (-	Day 15 (-1)	Day 22 (-1)	Day 27	Day 29 (-1)	Day 31
Informed consent	X										
Inclusion/exclusion	X	X									
Continuation criteria				X c		X c	X c	X c		X c	
Study drug administration				X		X	X	X		X	
Medical history	X										
Physical exam		X		X c		X c	X c	X c		X c	
Height		X									
Weight		X		X c		X c	X c	X c		X c	
Vital Signs d		X		X c		X c	X c	X c		X c	
ECOG performance status		X		X c		X c	X c	X c		X c	
HLA typing e	X										
Serum pregnancy test f	X			X c							
Serology g	X										
Hematology/ serum chemistry h		X		$X^{c,i}$		X c	X c	X c		X c	
Urinalysis		X		$X^{c,i}$			X c			X c	
12-lead ECG		X		X c,i						X c	
DTH skin test injection			X j	$X^{j,k}$					$X^{j}$	$X^{j,k}$	

Table 1: Schedule of Assessments for Screening and Vaccine Induction Phase – Part 1 (Continued)

		ening					Induction Phase a,t				
	within	within 7		1 st dose		2 nd dose	3 rd dose	4 th dose		5 th dose	
	14/21 days before 1 st dose (-1 – -14/-21)	days before 1 st dose (-17)	Day -2	Day 1 (-1)	Day 3	Day 8 (-1)	Day 15 (-1)	Day 22 (-1)	Day 27	Day 29 (- 1)	Day 31
DTH skin test evaluation 				X m	X n					X m	X n
Blood sample for CTL		X		X c		X c	X c	X c		X c	
Blood sample for Anti-WT1 antibody				X c			X c			X c	
Blood sample for PBMC isolation				X c						X c	
Blood sample for retrospective biomarker analyses				X c,o	Xº	Xc	X c			X°	

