IHC tumor samples		$X^{p,q}$									
Tumor assessment	X r									X s	
Adverse events		•	•	•	•	•	•	•	•	•	-
Concomitant medications											-

Abbreviations: AML = acute myeloid leukemia, CA-125 = cancer antigen 125, CTL = cytotoxic T lymphocyte induction activity, DTH = delayed-type hypersensitivity reactivity, ECG = electrocardiogram, ECOG = Eastern Cooperative Oncology Group, FSH = follicle-stimulating hormone, HLA = human leukocyte antigen, IHC = immunohistochemistry.

irRC = immune-related response criteria, IWG = International Working Group response criteria in acute myeloid leukemia, MRI = magnetic resonance imaging,
PBMC = peripheral blood mononuclear cell, PET = positron-emission tomography, RT-PCR = reverse transcriptase-polymerase chain reaction, SPECT = single-photon emission computed tomography, WT1 = Wilms' tumor gene product 1

- a Additional dosing windows are provided for patients who may need to recover from intercurrent medical conditions (see Section 8.3.2.1 of protocol).
- b All patients should complete an End of Study visit (see Table 2) within 28 days after the last dose of study drug and prior to the start of alternate antineoplastic therapy.
- c Prior to study drug administration.
- d Includes systolic and diastolic blood pressures, pulse, respirations rate, and oral body temperature.
- e If HLA typing has been performed previously, these results may be used, otherwise HLA typing should be the first procedure performed during screening.
- f For females of child-bearing potential.
- g Includes hepatitis B and C, human immunodeficiency virus (HIV)-1, and HIV-2, if there are signs or symptoms suggestive of infection.
- h See Appendix IV of protocol for list of required laboratory tests at each visit.
- Assessment may be omitted if an assessment was performed within the previous 3 days. If there are multiple assessments the most recent ones should be used.
- j Perform DTH skin test injections approximately 48 hours (but no sooner than 24 hours) prior to the evaluation.
- k Perform DTH skin test injections immediately before administration of study drug.
- 1 If the DTH reactivity results in erythema with induration greater than 2 cm, or leads to ulceration of the skin test site, further DTH testing should not be conducted for the patient.

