- m Evaluation should be made on the planned dosing day, prior to study drug administration.
- n Evaluation should be approximately 48 hours (but no sooner than 24 hours) after the DTH skin test injection.
- $^{o}$  Samples obtained 6 hours (± 30 minutes) and 48 hours (± 6 hours) postdose.
- P In place of tumor tissue samples from a biopsy during screening, archived tumor tissue samples may be provided. Availability of tumor tissue samples should be determined during screening through provision of the accession number or other identification number. If necessary, the tumor tissue sample biopsy should be performed after study eligibility has been confirmed and before the first dose of study drug. The tumor tissue samples will only be provided to the sponsor for patients who receive study drug. In place of archival tumor tissue samples, patients with AML should have available a bone marrow aspirate and/or bone marrow biopsy with PCR for WT1 transcript performed before the first dose of study drug. Patients with AML should also have peripheral blood assessed for blasts and WT1 transcript.
- q IHC need not be performed for patients with AML provided RT-PCR for WT1 transcript is assessed.

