## 8.6.3.2. Immune Response

Peripheral blood samples will be obtained for evaluation of WT1 peptide-specific CTL induction activity by tetramer assay and WT1 serum antibody titer by enzyme-linked immunosorbent assay (ELISA), and for isolation of PBMCs. In addition, blood samples will be obtained and blood serum archived for possible analyses of other biomarkers, such as protein and microRNA, that may be important to the understanding of WT2725 but which have not yet been selected. These results may be presented in figures and/or patient data listings.

For DTH assessments, the number of patients who have an injection with WT2725 and control will be displayed before and after injection for each dose. The number and percentage for the reaction of positive and negative based on the number of patients who have injections may also be presented for the WT2725 versus negative control. The summary for all the dose will also be generated. The patients who have at least one injection will be present. The number of positive reaction for overall is counted for the patients who have at least one positive reaction during all the doses. The number of negative reaction for overall is counted for those patients who have all negative reaction during all the doses. The corresponding percentage will also be displayed similary for each dose. The results may also be presented in data listings.

For WT1 by RT-PCR tumor marker, the descriptive statistics have been provided for the baseline, at each post-baseline assessment and change from baseline by dose cohort, including the minimum and maximum of all the post-baseline assessments.

Immunohistochemistry in tumor tissue may be evaluated by expression of CD8+, Foxp3, HLA class I, and other measurements using tumor tissue samples obtained before the first dose. Due to the sparsity of the post-baseline data, post-baseline results will only be listed but not summarized. Continuous results will be summarized in a table with mean, standard deviation, median, quartiles, minimum, and maximum. Categorical variables will be summarized in a table with frequencies and percentages. Additionally, histograms of continuous results and bar plots of categorical results will be presented.

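### The all-dose DTH summary does not exclude the skin test read before the first dose, so a patient positive only before WT2725 counts the same as a converter

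*SAP*

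**What the plan says.** SAP section 6.3 lists DTH to the WT2725 peptide, at each assessment time, among the secondary measures of immune response. The analysis is in section 8.6.3.2.

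- **Per dose:** "the number of patients who have an injection with WT2725 and control will be displayed before and after injection for each dose". Positive and negative counts and percentages, WT2725 against negative control, may also be shown.
- **All doses, positive:** "The number of positive reaction for overall is counted for the patients who have at least one positive reaction during all the doses".
- **All doses, negative:** "The number of negative reaction for overall is counted for those patients who have all negative reaction during all the doses".
- **Who is included:** "The patients who have at least one injection will be present".

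The schedules in section 6.1 (Tables 1 and 3) place a skin test injection on Day -2 in both parts of the study. It is read on Day 1 under a footnote that says "Evaluation should be made on the planned dosing day, prior to study drug administration". A second test is injected on Day 1 immediately before the first dose and read on Day 3. Another footnote to both tables says that after a reaction with induration above 2 cm, or ulceration, "further DTH testing should not be conducted for the patient".

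**The concern.** The Day 1 predose reading is taken before the patient has received any WT2725, so it is a baseline. The all-dose rule does not set it apart: one positive reading at any point makes the patient positive, and the negative group requires every reading to be negative. Prior reactivity to the peptide and reactivity induced by the vaccine therefore fall into the same count, in a row that readers will take as a summary of immune response.

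A second, weaker feature is that an any-positive rule may give a higher figure the more often a patient is tested, and the number of tests depends on time on study.

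**Working it through.** The documents state no expected DTH rate, sample size or power for this endpoint, so there is no figure to reproduce. The check is of the text first, then an illustration with assumed rates.

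**1. Does anything remove the Day 1 predose reading?**

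- Section 8 defines baseline as the last non-missing value before the first dose. That would make this reading the baseline, but the DTH rule never refers to baseline.
- Section 8.6.3 restricts most exploratory analyses to patients with a baseline and at least one posttreatment value. That selects patients; it does not drop the baseline reading from the count. It also differs from the at-least-one-injection rule in 8.6.3.2.
- Section 8.6.3.1, the neighbouring CTL rule, counts only post-baseline values, judged against baseline. The DTH rule has no such restriction.
- The per-dose results "will be displayed before and after injection for each dose", so the reading before dose 1 is part of the data being summarised.

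Nothing removes it.

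**2. Number of tests (Tables 1 to 4).** Injections fall on Days -2, 1, 27, 29, 83 and 85 and 48 hours before the End of Study visit, with readings on Days 1, 3, 29, 31, 85, 87 and End of Study. That makes 7 in each part, of which 1 precedes study drug. A patient leaving before Day 27 has at most 3: Day -2, Day 1 and End of Study.

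**3. Effect of baseline reactivity.** Let b be the assumed share positive on Day 1 predose, and q the assumed share of baseline-negative patients who become positive later.

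- SAP all-dose row: b + (1 - b)q.
- Converters over all patients: (1 - b)q. The difference is b.
- Converters over baseline-negative patients only: q.

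| b | SAP row, q = 0 | SAP row, q = 20% | Converters over all, q = 20% |
|---|---|---|---|
| 5% | 5% | 0.05 + 0.95 × 0.20 = 24% | 19% |
| 10% | 10% | 0.10 + 0.90 × 0.20 = 28% | 18% |
| 20% | 20% | 0.20 + 0.80 × 0.20 = 36% | 16% |

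With no vaccine effect, the chance that a cohort of n shows at least one positive patient from baseline reactivity alone is 1 - (1 - b)^n. For b = 5%, 10% and 20% this is 26.5%, 46.9% and 73.8% with n = 6, and 40.1%, 65.1% and 89.3% with n = 10.

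**4. Effect of the number of tests.** Let p be an assumed null positive rate per test. With k independent tests, any-positive is 1 - (1 - p)^k. With tests fully correlated within a patient, it is p for any k.

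| p | 3 tests | 7 tests |
|---|---|---|
| 5% | 5% to 1 - 0.95^3 = 14% | 5% to 1 - 0.95^7 = 30% |
| 10% | 10% to 1 - 0.90^3 = 27% | 10% to 1 - 0.90^7 = 52% |

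**The case against.** The strongest reply is that this is a wording gap in one descriptive row. The secondary endpoint is defined by assessment time, and the per-dose display would put the Day 1 predose result in its own cell. Tests around Days 29 and 85 (doses 5 and 9 in Part 1, doses 5 and 11 in Part 2) would also be shown. No test, confidence interval or decision uses the all-dose row. The wording about all the doses could mean on-treatment readings only. All of this limits the reach of the point. It does not settle what the row counts: the SAP does not say on-treatment only, and its display includes readings before dosing.

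Three stronger readings are tempting and are not supported.

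- **The Day 1 reading inflates the row for every baseline-positive patient.** A patient with persistent reactivity would be positive again later and be counted anyway. The Day 1 reading alone changes the status only of patients whose later tests are all negative or were not done. The stopping rule for strong reactions makes the second case possible. For the same reason, dropping that one reading would not be enough.
- **The row favours cohorts that stay on study longer.** The SAP plans no formal comparison of cohorts on DTH, and the documents do not show that cohorts differ in time on study.
- **Repeated testing pushes false positivity to 30% or 52%.** Those figures need seven independent tests in one person. Repeat tests with the same peptide are likely to be correlated, and under full correlation the gradient disappears.

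Nor do the documents show that baseline positivity occurs at all. The available protocol text is an amendment history, so a fuller DTH definition in the protocol body cannot be checked.

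**Conclusion.** The point holds for the all-dose DTH row. Followed as written, it counts a reading taken before any WT2725 and treats a patient positive only then as equal to a converter. Compared with a count of converters over the same patients, the excess equals the baseline positivity rate: 5, 10 or 20 percentage points if that rate is 5%, 10% or 20%. These rates are assumptions; if no patient is positive at baseline, the excess is zero.

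The dependence on the number of tests is a possibility whose size turns on an unknown within-patient correlation, so only the ranges above can be given. The primary objectives, safety and MTD, are not affected.

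**What to change.** Amend SAP section 8.6.3.2 as follows.

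1. Label the Day -2 test, read predose on Day 1, as the DTH baseline.
2. Define the all-dose row as patients negative at baseline and positive (WT2725 site positive, control negative) at one or more post-baseline tests.
3. Use as denominator patients with a baseline and at least one post-baseline reading, and reconcile this with section 8.6.3. State whether baseline-positive patients stay in it, since that decides between (1 - b)q and q.
4. Show baseline-positive patients separately, including any whose testing stopped after the Day 1 reading.
5. State whether the Day 3 reading is baseline or post-baseline. That test is placed immediately before dose 1 and read about 48 hours after it; if it is classed as post-baseline without comment, a test placed before any vaccine could count as conversion.
6. Read the existing per-dose results around Days 29 and 85 alongside the all-dose row. A conversion rule still counts any later positive, so it does not remove the dependence on the number of tests.

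The cost is SAP wording and a small programming change; no new data are needed. The reported positivity rate and the denominator may both fall.

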## 8.6.4. Additional Exploratory Endpoints

For solid tumor patients the following endpoints will be calculated as follows:

• Progression-free survival (PFS) is defined as the time in weeks from first dose date to the date of progression or the date of death due to any cause. Patients who are alive and have not progressed by the date of analysis data cut-off will be censored at the last free evaluable tumor assessment date based on investigator

assessment. Patients with missing protocol scheduled tumor assessment(s) prior to radiologic disease progression will be considered as having disease progression on the date of the actual assessment of disease progression.

- Time to progression (TTP) is defined as the time in weeks from first dose date to the date of observed disease progression. Patients who do not have disease progression by the date of analysis data cutoff will be censored at the date of last evaluable tumor assessment based on investigator assessment.
- Duration of response (DOR) is defined as the time in weeks from the first date of response to date of first progression of disease or death in the subset of patients with an objective response of irCR or irPR. Patients who respond and have not progressed (as evaluated by investigator assessment) while on study or die will be censored at the date of their last evaluable tumor assessment. Duration of response is calculated only for patients with an objective response.

For AML patients, the following endpoints will be calculated as follows:

- Relapse is defined as
  - an investigator assessment following CRc becoming PR, PRi, PD, or No Response. The date of the worsening disease assessment will be the relapse date; or
  - an investigator assessment following PR or PRi becoming PD or No Response. The date of the worsening disease assessment will be the relapse date
- Duration of CRc: Time, in weeks, from first CRc until documented relapse and is only defined for patients who achieve CRc. Patients who die without report of relapse are considered non-events and censored at their last relapse-free disease assessment date. Patients who come off study for an allogeneic HSCT will be considered non-events and censored at the time of treatment discontinuation. Other patients who do not relapse on study are considered non-events and censored at the last relapse-free assessment date.
- Duration of disease control: Time, in weeks, from first of either PR, PRi or CRc until documented relapse of any type and is only defined for patients who achieve CRc, PR or PRi. Patients who die without report of relapse are considered non-events and censored at their last relapse-free disease assessment date. Patients who come off study for an allogeneic HSCT will be considered non-events and censored at the time of treatment discontinuation. Other patients who do not

relapse on study are considered non-events and censored at the last relapse-free assessment date.

 Time to progression for AML (TTPAML) is defined as the time in weeks from first dose date to the date of observed disease progression (see Section 8.6.2.2).
 Patients who do not have disease progression by the date of analysis data cutoff will be censored at the date of last evaluable disease assessment based on investigator assessment.

For all patients, and by disease group, the following endpoints will be calculated as follows:

- Date of last contact will be defined as the latest of the treatment discontinuation date, last dosing administration date, last disease assessment date, end of study or the death date.
- Overall survival (OS): Time, in months, from first dose date until the date of death. Patients who do not die are censored at their date of last contact. Survival status is captured after the end of the treatment period and is also considered in determining overall survival.
- The specified time-to-event endpoints will be summarized graphically with Kaplan-Meier (KM) estimates of the survivor function and the number of patients at risk for selected timepoints. Additionally, the figures will include the median of the survival distribution and the 95% CI generated using the method of Brookmeyer and Crowley (Brookmeyer-1982). Time-to-event endpoint data will be listed grouped by tumor group. Each of the KM figures will be repeated for the Safety population as additional exploratory analyses.

For all the KM plots, the SAS output will be saved in Statistics Appendix in TFL.

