# 6.5. Additional Exploratory Endpoints

Progression-free survival (PFS), time to progression (TTP) and duration of response will be summarized for solid tumor patients. Duration of Composite Complete Remission (CRc), duration of response (CRc + partial remission [PR]), and time to progression for AML (TTPAML) will be summarized for AML patients. Overall survival (OS) will be summarized for all patients and by disease category (solid tumor vs. AML).

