- Unconfirmed irPD = Any irPD record after study day 1 and no record of irPD confirmed 4 weeks after, which include the situation that the PI can discontinue a patient from the study for the reason of PD without confirmation of PD after 4 weeks if patients have rapid symptomatic progression accompanied by a decline in performance status.

The assessment made by the investigator will be used for all summaries.

Best response is defined to be the best irRC response (irCR > irPR > irSD > irPD) evaluated after dosing until treatment discontinuation. Patients without post-baseline evaluations will be considered as unevaluable. Additional categories are defined for response (irCR + irPR) and disease control (irCR + irPR + irSD).

Tables will summarize the number and percentage of the best overall tumor response for each category by dose cohort, the number, percentage, and Wilson Score 95% CI will also be presented for the response categories of irCR, response, and disease control.

The percent change in tumor burden from baseline will be presented at each posttreatment tumor assessment graphically and in patient data listings. Percent change will be calculated as 100\*[(current tumor burden - baseline tumor burden)/baseline tumor burden]. The best change, i.e., the minimum of percent change from baseline for each patient will be displayed in a waterfall plot.

A by-patient listing of irRC assessment will be provided.

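### SAP 8.6.4 gives responder deaths two conflicting roles in solid-tumor DOR, leaves the AML duration of response named in 6.5 undefined, and shows AML remission durations only with deaths censored

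*SAP*

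**What the plan says.** **Solid tumors, SAP 8.6.4.** DOR runs "from the first date of response to date of first progression of disease or death in the subset of patients"; that subset is the patients who reach irCR or irPR. The censoring sentence that follows reads "Patients who respond and have not progressed (as evaluated by investigator assessment) while on study or die will be censored" at the last evaluable tumor assessment. PFS, in the same list, counts death from any cause as an event.

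**AML endpoints, SAP 6.5 and 8.6.4.** Section 6.5 names three: duration of CRc, "duration of response (CRc + partial remission [PR" (closing brackets cut), and time to progression. Section 8.6.4 defines duration of CRc, duration of disease control and time to progression. The second of these "is only defined for patients who achieve CRc, PR or PRi". Section 8.6.2.2 uses the same grouping for its AML disease control category (CR, CRi, PR and PRi).

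**Deaths in the AML durations, SAP 8.6.4.** The definitions of duration of CRc and of duration of disease control each carry the sentence "Patients who die without report of relapse are considered non-events and censored at their last relapse-free disease assessment date". Patients who leave for an allogeneic HSCT are censored at treatment discontinuation. All time-to-event endpoints are shown as Kaplan-Meier curves with a median and 95% CI. No competing-risk method is mentioned.

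**The concern.** The three points differ in kind.

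1. The DOR text assigns death to both sides of the event flag. Two programmers could each follow one sentence faithfully and report different medians.
2. A reader who takes the endpoint list from 6.5 will look for an AML duration of response that 8.6.4 does not define, and will find an endpoint that 6.5 does not list. The two populations differ by patients whose best remission is PRi. Under 8.6.2.2, PR requires blood counts to normalise and PRi does not, so the PRi rule decides who enters the endpoint.
3. A patient who dies in remission cannot relapse later. Kaplan-Meier with that death censored estimates time to relapse as though death did not remove patients from risk. Read as time alive in remission, the curve is too favourable. Some of these deaths may also be relapses nobody detected, because the AML response categories rest mainly on marrow blasts and marrow sampling is not on a fixed protocol schedule.

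**Working it through.** The documents give no median, event count or hazard for these endpoints, so there is no planned figure to reproduce. The first two points are textual checks; the third is sized under stated assumptions.

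**1. DOR.** Take a responder who dies without progression. Under the definition sentence this is an event at the date of death. Under the censoring sentence, read literally ("while on study or die will be censored at the date of their last evaluable tumor assessment"), it is a non-event at an earlier date. Both the flag and the time differ, and nothing in 8.6.4 says which sentence governs.

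**2. AML endpoint names and membership.**

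| Endpoint | In 6.5 | Defined in 8.6.4 |
|---|---|---|
| Duration of CRc | yes | yes |
| Duration of response (CRc + PR) | yes | no |
| Duration of disease control (CRc, PR or PRi) | no | yes |
| Time to progression, AML | yes | yes |

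One of the three endpoints in 6.5 is mismatched. A patient whose best remission is PRi is outside the 6.5 endpoint and inside the 8.6.4 endpoint.

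**3. Size of the death-censoring effect (illustrative).** Let λ be the relapse hazard and μ the hazard of death without relapse, both constant.

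- Median with deaths censored: ln 2 / λ.
- Median time to relapse or death: ln 2 / (λ + μ).
- Ratio: (λ + μ) / λ = 1 + μ/λ.
- With f = μ / (λ + μ), the share of first events that are deaths, the same ratio is 1 / (1 − f).

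| f (assumed) | μ/λ | Ratio | True median 12 weeks becomes | True median 24 weeks becomes |
|---|---|---|---|---|
| 10% | 0.11 | 1.11 | 13.3 | 26.7 |
| 20% | 0.25 | 1.25 | 15.0 | 30.0 |
| 30% | 0.43 | 1.43 | 17.1 | 34.3 |
| 50% | 1.00 | 2.00 | 24.0 | 48.0 |

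A simulation of 200,000 patients per setting added visits, with relapse found at the next visit and deaths censored at the last one. With a true median of 24 weeks, the death-as-event median was 24. The death-censored medians for f = 10%, 20%, 30% and 50% were 28, 32, 36 and 48 weeks with 4-week visits, and 32, 32, 40 and 48 with 8-week visits. Part of the gap is rounding to the visit grid. With a true median of 12 weeks and 8-week visits, the two medians were equal (16 weeks) at f = 10% and 20%, so the median does not always move.

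A small made-up set shows the mechanics. Six responders relapse at weeks 8, 16, 24 and 32; two others die at weeks 14 and 19, last seen in remission at weeks 12 and 16.

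- Deaths censored: the curve is 5/6 at week 8, then 5/6 × 3/4 = 0.625 at week 16, then 0.625 × 1/2 = 0.3125 at week 24. The median is 24 weeks.
- Deaths as events: half of the six have failed by week 16. The median is 16 weeks.

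One caution on direction. Because censoring is set back to the last assessment, a relapse falling between that date and the death is divided by a smaller risk set, which makes its step larger. With a handful of responders this can partly offset the effect, so the upward direction is a tendency and not a guarantee in every dataset.

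**The case against.** **The AML rule is a choice, not an error.** Both durations run to documented relapse, and the death rule is explicit, identical in both and programmable. The two time-to-progression endpoints are also progression-only, and OS covers death from any cause. This stands. A reader might infer that the AML estimates are simply biased; that follows only if the target is time alive in remission, which the SAP does not state. The documents support adding an analysis, not calling the existing one wrong. Nor do they plan any comparison of AML durations with solid-tumor DOR.

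**Marrow surveillance is better than it may look.** A reader of Tables 1 and 3 might infer that marrow is taken after baseline only when clinically indicated, so that these deaths must include missed relapses. Tables 2 and 4 add that, with no other measurable disease, marrow follows a post-transplant or site schedule, and blood is assessed at least every 4 weeks. What remains is that some deaths may be undetected relapses.

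**PRi may be rare or common.** Because the Protocol's Amendment No. 4 expects baseline cytopenias in AML, one might infer that most partial remissions would be PRi. No document gives the PR/PRi split or counts at remission.

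**The AML label.** The irRC category "disease control (irCR + irPR + irSD" (closing bracket cut) includes stable disease and the AML one does not. One might infer that the AML label is wrong. The on-treatment AML categories in 8.6.2.2 contain no stable disease, so renaming is a preference.

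**DOR is probably a drafting slip.** The definition sentence suggests that censoring was meant for responders who have neither progressed nor died. That is likely, but the sentence still has to be corrected.

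**Small numbers.** About 60 to 80 patients are to be dosed in total, and only AML patients who reach remission enter these endpoints. Medians may not be estimable. This limits how much the third point can matter.

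**Conclusion.** Two defects stand as written: the DOR censoring sentence contradicts the DOR definition, and one of the three AML endpoints in 6.5 has no definition in 8.6.4 while an unlisted endpoint takes its place. Duration of CRc and AML time to progression already agree.

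The third point is an inexpensive improvement. With deaths censored under Kaplan-Meier, the AML curves and medians tend to overstate time alive in remission when patients die without reported relapse. The factor 1 / (1 − f), from 1.11 at f = 10% to 2.00 at f = 50%, rests on constant hazards and on values of f that the documents do not supply. It is a large-sample result applied to what will be few responders.

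All of this concerns exploratory, descriptive endpoints. The DLT and MTD analyses, the response rates and OS are unaffected.

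**What to change.** 1. **DOR (8.6.4).** Reword the censoring sentence so that it applies only to responders who have neither progressed nor died, still at the last evaluable tumor assessment. Cost: one sentence.
2. **AML endpoint (6.5, 8.6.2.2, 8.6.4).** Choose one endpoint, state once whether PRi counts, and use the same name and definition in all three sections. Cost: wording only.
3. **AML durations (8.6.4).** Keep the relapse-only estimate. Beside it, show either duration to relapse or death, or cumulative incidence of relapse with death as a competing event. State two rules for the added analysis:
   - How deaths after a patient leaves the study are treated. Survival contact continues every 3 months after the End of Study visit. Without a rule, late deaths become events while living patients who left without relapse stay censored at an earlier date.
   - How allogeneic HSCT is treated, since the present rule covers only the relapse-only estimate.

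No new data are needed, because death dates are already collected for OS. The cost is a little more programming than a changed flag, because of the two rules above. The relapse-or-death durations can be expected to be shorter than the relapse-only ones.
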